Normal	xx (xx.x)	xx (xx.x)	xx (xx.x)	xx (xx.x)	
High	xx (xx.x)	xx (xx.x)	xx (xx.x)	xx (xx.x)	
Missing	xx (xx.x)	xx (xx.x)	xx (xx.x)	xx (xx.x)	

Note: Baseline is defined as last available value prior to ther first dose of study medication for a particular treatment. The worst value is defined as the maximum on-study value. High = Higher than the upper limit of the normal range, Low = Lower than the lower limit of the normal range, Normal = within the lower and upper limits of the normal range. Percentages are based on the number of subjects in each treatment/analysis group.

Source Data: Listing 2.7.1

Table 1.7.2.1
Renal Function Tests
Safety Population

Repeat of 1.7.1.1

Note: Baseline is defined as last available value prior to ther first dose of study medication for a particular treatment.

¹Change from baseline: post-baseline value - baseline value. For the change from baseline, only subjects with a value at both the baseline visit and the specific post-baseline visit are included. Source Data: Listing 2.7.2

<DIRECTORY PATH>PROGRAM NAME Executed: DDMMMYYYY hh:mm

Parameters: Blood Urea Nitrogen, Creatinine, Estimated GFR - MDRD, Estimated GFR - Cockcroft-Gault

Table 1.7.2.2

Renal Function Tests - Shifts from Baseline to Worst On-Study Value
Safety Population

Repeat of 1.7.1.2

Source Data: Listing 2.7.2

Note: Baseline is defined as last available value prior to ther first dose of study medication for a particular treatment. The worst value is defined as the minimum on-study value. High = Higher than the upper limit of the normal range, Low = Lower than the lower limit of the normal range, Normal = within the lower and upper limits of the normal range. Percentages are based on the number of subjects in each treatment/analysis group.

Table 1.8
Vital Signs
Safety Population

Parameter: XXXXX (units)

·	·	340mg	≥340mg	
	Placebo	Placebo ADS-5102		ADS-5102
	(N=xx)	(N=xx)	(N=xx)	(N=XX)
Baseline				
n	XX	xx	xx	XX
Mean	XX.X	XX.X	xx.x	XX.X
SD	XX.XX	xx.xx	xx.xx	XX.XX
Median	XX.X	xx.x	xx.x	XX.X
Min, Max	XX, XX	XX, XX	XX, XX	XX, XX
linimum				
n	XX	xx	xx	XX
Mean	XX.X	XX.X	XX.X	XX.X
SD	XX.XX	XX.XX	XX.XX	XX.XX
Median	XX.X	XX.X	XX.X	XX.X
Min, Max	XX, XX	XX, XX	XX, XX	xx, xx
Maximum				
n	XX	xx	xx	XX
Mean	XX.X	XX.X	XX.X	XX.X
SD	xx.xx	xx.xx	xx.xx	XX.XX
Median	XX.X	XX.X	XX.X	XX.X
Min, Max	xx, xx	xx, xx	xx, xx	XX, XX

Note: Baseline is defined as last available value prior to ther first dose of study medication for a particular treatment. For the change from baseline, only subjects with a value at both the baseline visit and the specific post-baseline visit are included.

Source Data: Listing 2.8

<DIRECTORY PATH>PROGRAM NAME Executed: DDMMMYYYY hh:mm

Parameters: Sitting Systolic BP, Sitting Diastolic DP, Heart Rate

Table 1.8
Vital Signs
Safety Population

Parameter: XXXXX (units)

		340mg	≥340mg	
	Placebo	ADS-5102	ADS-5102	ADS-5102
	(N=XX)	(N=xx)	(N=XX)	(N=xx)
Change from Baseline				
(Minimum)				
n	XX	XX	XX	XX
Mean	XX.X	XX.X	XX.X	XX.X
SD	XX.XX	XX.XX	XX.XX	XX.XX
Median	XX.X	XX.X	XX.X	XX.X
Min, Max	xx, xx	XX, XX	xx, xx	XX, XX
Change from Baseline				
(Maximum)				
n	XX	xx	XX	XX
Mean	XX.X	XX.X	XX.X	XX.X
SD	XX.XX	xx.xx	xx.xx	XX.XX
Median	XX.X	XX.X	XX.X	XX.X
Min, Max	xx, xx	xx, xx	xx, xx	XX, XX

Note: Baseline is defined as last available value prior to ther first dose of study medication for a particular treatment. For the change from baseline, only subjects with a value at both the baseline visit and the specific post-baseline visit are included.

Source Data: Listing 2.8

<DIRECTORY PATH>PROGRAM NAME Executed: DDMMMYYYY hh:mm

Parameters: Sitting Systolic BP, Sitting Diastolic DP, Heart Rate

- Listing 2.1.1 Subject Identification Lookup Table Safety Population
- Listing 2.1.2 Study Withdrawal and Reason for Withdrawal Safety Population
- Listing 2.1.3 Study Drug Discontinuation and Reason for Discontinuation Safety Population
- Listing 2.2 Demographics and Other Baseline Characteristics Safety Population
- Listing 2.3.1 Parkinson's Disease History Safety Population
- Listing 2.3.2 Parkinson's Disease-Related Baseline Characteristics (Part I) Safety Population
- Listing 2.3.3 Parkinson's Disease-Related Baseline Characteristics (Part II) Safety Population
- Listing 2.4 Prior and Concomitant Medications Safety Population
- Listing 2.6.1 Adverse Events Safety Population
- Listing 2.6.2 Adverse Events Leading to Study Drug Dose Reduction Safety Population
- Listing 2.6.3 Adverse Events Leading to Study Drug Discontinuation Safety Population
- Listing 2.7.1 Laboratory Results Liver Function Tests Safety Population
- Listing 2.7.2 Laboratory Results Renal Function Tests Safety Population
- Listing 2.8 Vital Sign Results Safety Population

Listing 2.1.1
Subject Identification Lookup Table
Safety Population

Subject Identifier	Unique Subject Identifier	Study Identifier	Study Subject Identifier	
XXXXX-XX-XXX	ADS-XXX-XXXXX-XX	AM201	XXX	
	ADS-XXX-XXXXX-XX-XXX	PD302	XX-X-XXX	
XXXXX-XX-XXX	ADSXXXXXXXX-XX-XXX	PD301	XX-X-XXX	
XXXXX-XX-XXX	ADSXXXXXXXX-XX-X-XXX	PD302	XX-X-XXX	

Listing 2.1.2
Study Withdrawal and Reason for Withdrawal
Safety Population

Subject Identifier	Study Identifier	Treatment	First Dose Date/ Last Dose Date/	Subject Completed Study	Reason for Not Completing Study
XXXXX-XX-XXX	XXXXX	Placebo	DDMMMYYYY/ DDMMMYYYY	Y	
	XXXXX	340mg ADS-5102	DDMMMYYYY/ DDMMMYYYY	N	INTOLERABLE OR UNACCEPTABLE AES
XXXXX-XX-XXX	XXXXX	260mg ADS-5102	DDMMMYYYY/ DDMMMYYYY	Y	
XXXXX-XX-XXX	XXXXX	420mg ADS-5102	DDMMMYYYY/ DDMMMYYYY	N	NON-COMPLIANCE WITH STUDY DRUG

Listing 2.1.3
Study Drug Discontinuation and Reason for Discontinuation
Safety Population

Subject Identifier	Study Identifier	Treatment	First Dose Date/ Last Dose Date/ Treatment Duration (Days) ¹	Subject Completed Treatment	Reason for Not Completing Treatment
XXXXX-XX-XXX	XXXXX	Placebo	DDMMMYYYY/ DDMMMYYYY/ XX	Y	
	XXXXX	340mg ADS-5102	DDMMMYYYY/ DDMMMYYYY/ XX	N	INTOLERABLE OR UNACCEPTABLE AES
XXXXX-XX-X-XXX	XXXXX	260mg ADS-5102	DDMMMYYYY/ DDMMMYYYY/ XX	Y	
XXXXX-XX-XXX	XXXXX	420mg ADS-5102	DDMMMYYYY/ DDMMMYYYY/ XX	N	NON-COMPLIANCE WITH STUDY DRUG

¹ Treatment duration is defined as (Last dose date - First dose date) + 1.

Listing 2.2

Demographics and Other Baseline Characteristics

Safety Population

Subject Identifier	Study Identifier	Treatment	Age(yrs)/ Sex ¹ / Race ² / Ethnicity ³	Country/ ³ Geographic Region	Height(cm)/ Weight(kg)/ BMI(kg/m ²)	Baseline Estimated GFR (mL/min/1.73m2)	Baseline MAO-B Inhibitor Baseline Dopamine Agonist	
XXXXX-XX-X-XXX	XXXXX	Placebo	50/ M/ W/ HL	Canada/ North America	xxx.x/ xxx.x/ xx.x	xx.x	Y/N	Y
	XXXXX	340mg ADS-5102	51/ M/ W/ HL	Canada/ North America	xxx.x/ xxx.x/ xx.x	xx.x	Y/N	Υ
XXXXX-XX-XXX	XXXXX	260mg ADS-5102	60/ F/ O/ NHL	Austria/ European Union	xxx.x/ xxx.x/ xx.x	xx.x	Y/Y	N
XXXXX-XX-XXX	XXXXX	420mg ADS-5102	65/ M/ PI/ NHL	United States/ North America	xxx.x/ xxx.x/ xx.x	xx.x	N/N	И

Note: BMI = Body mass index, DBS = Deep Brain Stimulation

¹ F = Female, M = Male

 $^{^2}$ AI = American Indian or Alaska Native, AS = Asian, B = Black or African American, PI = Native Hawaiian or Other Pacific Islander, W = White, O = Other

³ HL = Hispanic or Latino, NHL = Not Hispanic or Latino

Listing 2.3.1
Parkinson's Disease History
Safety Population

Subject Identifier	Study Identifier	Treatment	Age at PD Diagnosis (yrs.)	Time Since PD Diagnosis (yrs.) ¹	Age at Start of Levodopa Treatment (yrs.)	Duration of Levodopa Treatment (yrs.) ¹	Duration of LID (yrs.) ¹	Baseline Levodopa Dose (mg) ²
XXXXX-XX-X-XXX	XXXXX	Placebo	XX	X	X	X • X	X . X	XX.X
	XXXXX	340mg ADS-5102	XX	X	X	X . X	X . X	XX.X
XXXX-XX-XXX	XXXXX	260mg ADS-5102	XX	X	X	X . X	X . X	XX.X
XXXXX-XX-XXX	XXXXX	420mg ADS-5102	XX	X	X	X . X	X . X	XX.X

Note: PD = Parkinson's disease, LID = Levodopa-induced dyskinesia, # indicates an imputed date.

¹Time since Parkinson's disease diagnosis = (Analysis Day 1 - Date of diagnosis of Parkinson's disease)/ 365.25. When only the month and year of diagnosis are available, the 15th day of the indicated month is assumed, and when only the year of diagnosis is available, July 1 of the indicated year is assumed. A similar algorithm is used for duration of levodopa treatment, and duration of levodopa-induced dyskinesia.

 2 Baseline total levodopa dosage is defined as the levodopa medication (any preparation) with last start date prior to first dose of study medication.

Listing 2.3.2
Parkinson's Disease-Related Baseline Characteristics (Part I)
Safety Population

Subject Identifier	Study Identifier	Treatment	MDS-UPDRS Part I	MDS-UPDRS Part II	MDS-UPDRS Part III	MDS-UPDRS Combined	MDS-UPDRS Part IV
XXXXX-XX-X-XXX	XXXXX	Placebo	XX	Х	Х	X . X	X . X
	XXXXX	340mg ADS-5102	XX	X	X	X.X	X • X
XXXXX-XX-XXX	XXXXX	260mg ADS-5102	XX	X	X	X.X	X • X
XXXXX-XX-XXX	XXXXX	420mg ADS-5102	XX	X	Х	X.X	X.X

Note: PD = Parkinson's disease, LID = Levodopa-induced dyskinesia, # indicates an imputed date.

¹Time since Parkinson's disease diagnosis = (Analysis Day 1 - Date of diagnosis of Parkinson's disease)/ 365.25. When only the month and year of diagnosis are available, the 15th day of the indicated month is assumed, and when only the year of diagnosis is available, July 1 of the indicated year is assumed. A similar algorithm is used for duration of levodopa treatment, and duration of levodopa-induced dyskinesia.

 2 Baseline total levodopa dosage is defined as the levodopa medication (any preparation) with last start date prior to first dose of study medication.

Listing 2.3.3
Parkinson's Disease-Related Baseline Characteristics (Part II)
Safety Population

Subject	Study		MDS-UPDRS Part IV	MDS-UPDRS Part IV	MMSE	Hoehn and
Identifier	Identifier	Treatment	Item 4.1	Item 4.2	Score	Yahr Stage
XXXXX-XX-X-XXX	XXXXX	Placebo	XX	Х	Х	X • X
	XXXXX	340mg ADS-5102	XX	X	X	X • X
XXXXX-XX-XXX	XXXXX	260mg ADS-5102	XX	X	X	X • X
XXXXX-XX-XXX	XXXXX	420mg ADS-5102	XX	X	Х	X • X

Listing 2.4 Prior and Concomitant Medications Safety Population

Subject Identifier	Study Identifier	Treatment	ATC TERM/ PREFFERED TERM/ MEDICATION REPORTED	Indication	Start Date/ Stop Date/ Flag ¹	Dose/ Unit/ Route/ Frequency
XXXXX-XX-X-XXX	XXXXX	Placebo	XXXXXXXXXXXXX/ XXXXXXXXXXXXXXXXXX/ XXXXXX	XXXXXXXXX	DDMMMYYYY/ Ongoing/ P	XXXXX/ XXXXXX/ XXXXXXX
XXXXX-XX-XXX	XXXXX	340mg ADS-5102	XXXXXXXXXXXXXX/ XXXXXXXXXXXXXXXXXXXXXX	XXXXXXXXX	DDMMMYYYY/ DDMMMYYYY/ P/C	XXXXX/ XXXXXX/ XXXXXX/ XXXXXX

Note: Freq = Frequency

Prior medications are defined as medications taken within the 30 days that started and stopped prior to Analysis Day 1 (first day of study drug administration).

¹P=Prior medication, C=Concomitant medication

Prior and concomitant medications were coded with the WHO Drug dictionary dated MAR 2014.

Listing 2.6.1 Adverse Events Safety Population

Subject Identifier	Study Identifier	Treatment	System Organ Class/ Preferred Term/ VERBATIM TERM	Start Date (Day)/ Stop Date (Day)/ Duration (Days) ¹	Serious/ Intensity/ Causality/ Outcome/ Action Taken
XXXXX-XX-X-XXX	xxxxx	Placebo	XXXXXXXXXXXXXXXXXX/ XXXXXXXXXXXXXXXXXX	DDMMMYYYY (xx)/ DDMMMYYYY (xx)/ XX	Yes/ Mild/ Not Related/ Recovered/Resolved/ Dose not changed
XXXXX-XX-XXX	XXXXX	340mg ADS-5102	XXXXXXXXXXXXXXXXX/ XXXXXXXXXXXXXXXXX/ XXXXXX	DDMMMYYYY (xx)/ DDMMMYYYY (xx)/ XX	No/ Moderate/ Related/ Recovered/Resolved with sequelae/ Drug Interrupted
xxxxx-xx-xxx	XXXXX	260mg ADS-5102	XXXXXXXXXXXXXXXXX/ XXXXXXXXXXXXXXXX/ XXXXXX	DDMMMYYYY (xx)/ DDMMMYYYY (xx)/ XX	Yes/ Severe/ Not Related/ Unknown/ Drug Withdrawn
xxxxx-xx-xxx	XXXXX	420mg ADS-5102	XXXXXXXXXXXXXXXXX/ XXXXXXXXXXXXXXXXXXX	DDMMMYYYY (xx)/ DDMMMYYYY (xx)/ XX	No/ Mild/ Related/ Not Recovered/Not resolved/ Other
xxxxx-xx-xxx	XXXXX	340mg ADS-5102	XXXXXXXXXXXXXXXXX/ XXXXXXXXXXXXXXXXX XXXXXX	DDMMMYYYY (xx)/ DDMMMYYYY (xx)/ XX	Yes/ Severe/ Not Related/ Fatal/ Dose not changed

¹Duration (Days = Stop date - Start date + 1). Adverse events are coded using MedDRA Version 17.0.

<DIRECTORY PATH>PROGRAM NAME Executed: DDMMMYYYY hh:mm

Listing 2.6.2

Adverse Events Leading to Study Drug Dose Reduction

Safety Population

Same layout as X.X

¹Duration (Days = Stop date - Start date + 1). Adverse events are coded using MedDRA Version 17.0.

<DIRECTORY PATH>PROGRAM NAME Executed: DDMMMYYYY hh:mm

Listing 2.6.3

Adverse Events Leading to Study Drug Discontinuation
Safety Population

Same layout as X.X

¹Duration (Days = Stop date - Start date + 1). Adverse events are coded using MedDRA Version 17.0.

<DIRECTORY PATH>PROGRAM NAME Executed: DDMMMYYYY hh:mm

Listing 2.7.1
Laboratory Results - Liver Function Tests
Safety Population

Subject Identifier	Study Identifier	Treatment	Sample Date	Laboratory Test	Result	Units	Flag	Normal Range
XXXXX-XX-X-XXX	XXXXX	260mg ADS-5102	DDMMMYYYY	XXXXXXXXXXXXXXX	XXX.X	XXXXX		XXX.X-XXX.X
				XXXXXXXXXXXXXX	XXX.X	XXXXX		XXX.X-XXX.X
			DDMMMYYYY	XXXXXXXXXXXXXX	XXX.X	XXXXX	L*	XXX.X-XXX.X
				XXXXXXXXXXXXX	XXX.X	XXXXX		XXX.X-XXX.X
	XXXXX	340mg ADS-5102	DDMMMYYYY	xxxxxxxxxxxx	XXX.X	XXXXX	Н	XXX.X-XXX.X
				XXXXXXXXXXXXXX	XXX.X	XXXXX	Н	XXX.X-XXX.X
			DDMMMYYYY	XXXXXXXXXXXXXX	XXX.X	XXXXX		XXX.X-XXX.X
				XXXXXXXXXXXXXX	XXX.X	XXXXX		XXX.X-XXX.X

Note: H = Above Normal Range, L = Below Normal Range, N = Normal, * indicates minimum value

<DIRECTORY PATH>PROGRAM NAME Executed: DDMMMYYYY hh:mm

Listing 2.7.2

Laboratory Results - Renal Function Tests
Safety Population

Same as X.X

Listing 2.8
Vital Sign Results
Safety Population

Subject Identifier				Blood Pressure(mmHg)				
	Study Identifier	Treatment	Test Date	Sitting Systolic/Diastolic	Standing Systolic/Diastolic	Heart Rate (bpm)	Height (cm)	Weight (kg)
XXXXX-XX-X-XXX	XXXXX	260mg ADS-5102	DDMMMYYYY DDMMMYYYY	xx/xx xx/xx	xx/xx	xxx xxx	XXX.X	XX.X
		340mg ADS-5102	DDMMMYYYY	xx/xx	xx/xx	XXX	XXX.X	XX.X

[figure not shown]
Heart Rate (bpm=beats/minute)

ADS-5102 Integrated Summary of Safety

- Figure 3.1 Kaplan-Meier Analysis of Time to Study Drug Discontinuation Safety Population
- Figure 3.6.1.1 Kaplan-Meier Analysis of Time to Onset of AE (Neuropsychiatric) Safety Population
- Figure 3.6.1.2 Kaplan-Meier Analysis of Time to Onset of AE (Neuropsychiatric) by Gender Safety Population
- Figure 3.6.1.3 Kaplan-Meier Analysis of Time to Onset of AE (Neuropsychiatric) by Age Safety Population
- Figure 3.6.1.4 Kaplan-Meier Analysis of Time to Onset of AE (Neuropsychiatric) by Race Safety Population
- Figure 3.6.1.5 Kaplan-Meier Analysis of Time to Onset of AE (Neuropsychiatric) by Baseline Renal Function Safety Population
- Figure 3.6.1.6 Kaplan-Meier Analysis of Time to Onset of AE (Neuropsychiatric) by Weight Safety Population
- Figure 3.6.1.7 Kaplan-Meier Analysis of Time to Onset of AE (Neuropsychiatric) by Baseline MAO-B Inhibitor Medications Safety Population

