5.1 Safety

The Safety population will include all subjects who received at least one dose of study drug. It will be used for all safety analyses.

6 General Considerations for Statistical Analyses

Analysis Dataset Model (ADaM) datasets will be in accordance with the Clinical Data Interchange Standards Consortium (CDISC) standards and will be derived from the individual study data tabulation model (SDTM) and ADaM datasets for each study.

All tables, listings, figures and any other supportive SAS output will include in the footer explanatory notes that will indicate, at a minimum, the programming source (i.e., name, file path of the SAS program that generates the output), and run date.

Continuous data will be described using descriptive statistics as follows: number of observations (n), mean, median, standard deviation, minimum, and maximum, unless otherwise specified. All minimum and maximum values will be displayed with the same number of decimal places relative to the raw data, the mean and median will be displayed with one additional decimal place, and the standard deviation will be displayed with two additional decimal places.

Categorical data will be summarized by the number and percentage of subjects in each category. The denominator of all percentages will be the number of subjects in the population of interest, unless otherwise stated. When count data are presented, the percent will be suppressed when the count is zero in order to draw attention to the non-zero counts. A row denoted "Missing" will be included in count tabulations where necessary to account for dropouts and missing values. Non-zero percentages will be rounded to one decimal place, except 100% will be displayed without any decimal places.

In summary tables for categorical data, all categories will be presented if they are specified on the Case Report Form (CRF), or if categories are ordered intervals (e.g., age groups), regardless of whether data were present in each category, unless otherwise specified. For other categorical data (e.g., AEs and medications), only categories with non-zero frequencies will be presented.

Data will be displayed in all listings sorted by subject, study ID, and treatment. All summaries will be presented by treatment/analysis group, unless otherwise specified.

When no data are available for a table or appendix, an empty page with the title will be produced with suitable text (e.g., "There are no observations for this table/appendix.").

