7.2 Treatment Assignments and Analysis Groups

Treatment will be assigned using the treatment assignments from the individual studies.

Integrated listings will display the treatment received at the time the data was collected.

The following treatment/analysis groups will be included in summary tables, in the order shown:

- Placebo
- 340 mg ADS-5102
- \geq 340 mg ADS-5102
- ADS-5102

Individual summaries for 260 mg ADS-5102 and 420 mg ADS-5102 will not be included, but are available in the study results for ADS-PAR-AM201.

Since subjects may have received more than one treatment or ADS-5102 dose-level, they may be counted multiple times in summary tables, but will appear at most once in each treatment/analysis group and at most once in the overall column (where displayed).

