8.1 Disposition of Subjects

Disposition data from each study will be integrated, listed, and summarized for the Safety population.

A frequency table by treatment/analysis group and overall will include the number and percentage of subjects along with last available completion status.

A separate table will show the number (%) of subjects who withdrew and the primary reason for withdrawal, by treatment/analysis group and overall. The primary reasons of withdrawal reported by subjects will be presented in this table. The number (%) of subjects who discontinued study drug and the reason for early discontinuation will be summarized in a

separate table. Subjects may contribute more than one event to the summary table since it is possible for a subject to discontinue from more than one study. A footnote indicating the number of subjects with multiple study discontinuations will be included in the summary table.

The time to discontinuation of study drug will be analyzed. The time to discontinuation is defined as the number of days from the Analysis Day 1 date to the last dose of study drug for a particular treatment. Subjects will be censored if no early study drug discontinuation occurred. The median duration and the associated 95% confidence interval for each treatment group will be estimated using the Kaplan-Meier method (log-log transformation). Kaplan-Meier estimates of the survival function will be calculated and displayed graphically.

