- 1.6.12.3 Kaplan-Meier Analysis of Time to Onset of AE (Hallucinations) by Gender Safety Population
- 1.6.12.4 Kaplan-Meier Analysis of Time to Onset of AE (Hallucinations) by Age Safety Population
- 1.6.12.5 Kaplan-Meier Analysis of Time to Onset of AE (Hallucinations) by Race Safety Population
- 1.6.12.6 Kaplan-Meier Analysis of Time to Onset of AE (Hallucinations) by Baseline Renal Function Safety Population
- 1.6.12.7 Kaplan-Meier Analysis of Time to Onset of AE (Hallucinations) by Weight Safety Population
- 1.6.12.8 Kaplan-Meier Analysis of Time to Onset of AE (Hallucinations) by Baseline MAO-B Inhibitor Medications Safety Population
- 1.6.12.9 Kaplan-Meier Analysis of Time to Onset of AE (Hallucinations) by Baseline Dopamine Agonist Medications Safety Population
- 1.6.12.10 Kaplan-Meier Analysis of Time to Onset of AE (Hallucinations) by Baseline Levodopa Dose Safety Population
- 1.6.12.11 Kaplan-Meier Analysis of Time to Onset of AE (Hallucinations) Time since PD Diagnosis in Years Safety Population
- 1.6.12.12 Kaplan-Meier Analysis of Time to Onset of AE (Hallucinations) by Age at PD Diagnosis Safety Population
- 1.6.12.13 Kaplan-Meier Analysis of Time to Onset of AE (Hallucinations) by Prior Deep Brain Stimulation Safety Population
- 1.6.12.14 Kaplan-Meier Analysis of Time to Onset of AE (Hallucinations) by Geographic Region Safety Population
- Table 1.7.1.1 Liver Function Tests Safety Population
- Table 1.7.1.2 Liver Function Tests Shifts from Baseline to Worst On-Study Value Safety Population
- Table 1.7.2.1 Renal Function Tests Safety Population
- Table 1.7.2.2 Renal Function Tests Shifts from Baseline to Worst On-Study Value Safety Population Table 1.8 Vital Signs Safety Population

Table 1.1.1 Study Withdrawal and Reason for Withdrawal Safety Population

	Placebo (N=xx) n (%)	340mg ADS-5102 (N=xx) n (%)	≥340mg ADS-5102 (N=xx) n (%)	ADS-5102 (N=xx) n (%)	All (N=xx) n (%)
Subjects who withdrew from any study	xx (xx.x)	xx (xx.x)	xx (xx.x)	xx (xx.x)	xx (xx.x)
ADS-PAR-AM201	xx (xx.x)	xx (xx.x)	xx (xx.x)	xx (xx.x)	xx (xx.x)
ADS-AMT-PD301	xx (xx.x)	xx (xx.x)	xx (xx.x)	xx (xx.x)	xx (xx.x)
ADS-AMT-PD302	xx (xx.x)	xx (xx.x)	xx (xx.x)	xx (xx.x)	xx (xx.x)
Primary reason for withdrawal					
Subject discontinued study drug and wished to withdraw ¹					
Subject unwilling to proceed	xx (xx.x)	xx (xx.x)	xx (xx.x)	xx (xx.x)	xx (xx.x)
Subject consent was withdrawn	xx (xx.x)	xx (xx.x)	xx (xx.x)	xx (xx.x)	xx (xx.x)

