Subject lost to follow up	xx (xx.x)	xx (xx.x)	xx (xx.x)	xx (xx.x)	xx (xx.x)
Sponsor's decision	xx (xx.x)	xx (xx.x)	xx (xx.x)	xx (xx.x)	xx (xx.x)
Other	xx (xx.x)	xx (xx.x)	xx (xx.x)	xx (xx.x)	xx (xx.x)

Note: Percentages are based on the number of subjects in the Safety Population in each treatment/analysis group. If a subject withdrew from more than one study, both events will be counted.

¹Subjects who discontinued study drug were encouraged to complete all study assessments.

Source Data: Listing 2.1.2

Table 1.1.2
Study Drug Discontinuation and Reason for Discontinuation
Safety Population

			3	340mg	>	340mg				
	Pla	.cebo	AD	s-5102	AD	S-5102	AD	S-5102		All
	(N=	=xx)	(N=xx)	(N=xx)	(N=xx)	(N=xx)
	n	(%)	r	ા (%)	r	n (%)	r	n (%)	r	n (%)
Subjects who discontinued study drug	xx (xx.x)	XX	(xx.x)	XX	(xx.x)	XX	(xx.x)	XX	(xx.x)
from any study 1										
ADS-PAR-AM201	xx (xx.x)	XX	(xx.x)	XX	(xx.x)	XX	(xx.x)	XX	(xx.x)
ADS-AMT-PD301	xx (xx.x)	XX	(xx.x)	XX	(xx.x)	XX	(xx.x)	XX	(xx.x)
ADS-AMT-PD302	xx (xx.x)	XX	(xx.x)	XX	(xx.x)	XX	(xx.x)	XX	(xx.x)
Primary reason for study drug										
discontinuation										
Estimated glomerular filtration rate (eGFR) decreased to less than 50 mL/min/1.73m ²	xx (xx.x)	XX	(xx.x)	XX	(xx.x)	XX	(xx.x)	XX	(xx.x)
Estimated glomerular filtration rate decreased to less than 30 mL/min/1.73m ²	xx (xx.x)	XX	(xx.x)	XX	(xx.x)	XX	(xx.x)	XX	(xx.x
Adverse Events	xx (xx.x)	XX	(xx.x)	XX	(xx.x)	XX	(xx.x)	XX	(xx.x)
Positive pregnancy test	xx (xx.x)	XX	(xx.x)	XX	(xx.x)	XX	(xx.x)	XX	(xx.x)
Subject unwilling to proceed	xx (xx.x)	XX	(xx.x)	XX	(xx.x)	XX	(xx.x)	XX	(xx.x)
Subject consent was withdrawn	xx (xx.x)	XX	(xx.x)	XX	(xx.x)	XX	(xx.x)	XX	(xx.x)
Subject lost to follow up	xx (xx.x)	XX	(xx.x)	XX	(xx.x)	XX	(xx.x)	XX	(xx.x
Sponsor's decision	xx (xx.x)	XX	(xx.x)	XX	(xx.x)	XX	(xx.x)	XX	(xx.x
Other	xx (xx.x)	XX	(xx.x)	XX	(xx.x)	XX	(xx.x)	XX	(xx.x

Note: Percentages are based on the number of subjects in the Safety Population in each treatment group. If a subject withdrew from more than one study, both events will be counted.

Source Data: Listing 2.1.3

 $^{^{1}}$ Subjects who discontinued study drug early were encouraged to complete all study assessments.

Table 1.1.3
Kaplan-Meier Analysis of Time to Study Drug Discontinuation
Safety Population

	Placebo (N=xx)	340mg ADS-5102 (N=xx)	≥340mg ADS-5102 (N=xx)	ADS-5102 (N=xx)	All (N=xx)
Time to study drug discontinuation (Days)					
Event n (%)	xx (xx.x)	xx (xx.x)	xx (xx.x)	xx (xx.x)	xx (xx.x)

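### The by-study rows of SAP Tables 1.1.1 and 1.1.2 divide by the pooled column N, so equal PD301 stopping rates print about two to four times lower on ADS-5102 than on placebo

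*SAP*

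**What the plan says.** Both shells open with an any-study row (in Table 1.1.1, "Subjects who withdrew from any study"), followed by one row per study and then the reasons. Every cell is n (%) under Placebo, 340 mg, ≥340 mg, ADS-5102 or All, with a single N per column.

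The denominator in the Table 1.1.1 note is: "Percentages are based on the number of subjects in the Safety Population in each treatment/analysis group". In Table 1.1.2 it is: "Percentages are based on the number of subjects in the Safety Population in each treatment group". SAP Section 6 sets the default: "The denominator of all percentages will be the number of subjects in the population of interest, unless otherwise stated". No other denominator is stated for the by-study rows.

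On counting, both notes say: "If a subject withdrew from more than one study, both events will be counted". Section 8.1 explains that "Subjects may contribute more than one event to the summary table since it is possible for a subject to discontinue from more than one study" and adds: "A footnote indicating the number of subjects with multiple study discontinuations will be included in the summary table". That footnote is in neither shell. Section 7.2 sets a general rule that a subject "will appear at most once in each treatment/analysis group and at most once in the overall column".

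**The concern.** PD301 randomised 1:1 to placebo or 340 mg, so a reader will take the PD301 row as a comparison of those two arms. Under the stated rule the placebo count is divided by the AM201 and PD301 placebo subjects. The 340 mg count is divided by everyone who ever received 340 mg, most of them from open-label PD302. The active percentage is diluted by people who were never at risk of withdrawing from PD301 on active drug.

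The tables support a regulatory safety summary with no formal testing planned (SAP Sections 1 and 9), so the printed percentages are themselves the result. Safety-related drug discontinuation is a named safety outcome in Protocol Section 5.3.

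The PD302 placebo cell adds to the problem. It can only be zero, and Section 6 prints a zero count without its percentage, so it may read as no withdrawals when nobody was at risk.

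**Working it through.** The plan gives no rates or Ns for these rows, so there is no stated figure to reproduce.

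**Inputs**
- AM201: 83 randomised 1:1:1:1 (SAP Section 3) and 61 patients on the extended-release product (Protocol Section 4.4). So 83 − 61 = 22 on placebo and 61/3 ≈ 20.3 per active arm. Assumes all were dosed and the active arms were equal.
- PD301: 126 randomised 1:1 (SAP Section 3), so 63 per arm. Assumes all were dosed.
- PD302: up to 250, all on ADS-5102 (SAP Section 3; Protocol Sections 6.2 and 6.3). Section 4 plans the analysis at a database freeze, so N at that point is unknown; 150 and 250 are used as the range.
- Roll-over: not given. The range runs from none to full, meaning everyone already in the column is also in PD302.
- Rate: 13/63 = 20.6%, for illustration only.

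**Column Ns**
- Placebo: 22 + 63 = 85.
- 340 mg, PD302 = 250: 20.3 + 63 + 250 ≈ 333 with no roll-over, 250 with full roll-over. PD302 = 150: 233 to 150.
- ≥340 mg, PD302 = 250: 40.7 + 63 + 250 ≈ 354, down to 250. PD302 = 150: 254 to 150.
- ADS-5102, PD302 = 250: 61 + 63 + 250 = 374, down to 250. PD302 = 150: 274 to 150.

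**Formula**

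Printed % = within-study rate × (subjects of that study in the column ÷ pooled column N).

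At equal true rates, the printed active-to-placebo ratio does not depend on the rate. For PD301 it is (63/N) ÷ (63/85) = 85/N.

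**PD301 row, 13/63 in both arms, PD302 = 250**
- Placebo: 13/85 = 15.3%.
- 340 mg: 13/333 = 3.9% to 13/250 = 5.2%.
- True 340 mg rate needed to print level with placebo: 20.6% × 250/85 = 61% to 20.6% × 333/85 = 81%.

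**Printed active-to-placebo ratio when the true rates are equal** (each range runs from no to full roll-over)

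| Row and column | PD302 = 250 | PD302 = 150 |
|---|---|---|
| PD301, 340 mg | 0.26-0.34 | 0.36-0.57 |
| PD301, ≥340 mg | 0.24-0.34 | 0.34-0.57 |
| PD301, ADS-5102 | 0.23-0.34 | 0.31-0.57 |
| AM201, 340 mg | 0.24-0.31 | 0.34-0.52 |
| AM201, ≥340 mg | 0.44-0.63 | 0.62-1.05 |
| AM201, ADS-5102 | 0.63-0.94 | 0.86-1.57 |

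Splitting AM201 as 83/4 per arm changes little: at PD302 = 250 the 340 mg ratio is 0.25-0.34 in both rows.

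**With the study's own N**, 13/63 prints as 20.6% in both PD301 columns, a ratio of 1.00.

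**Double counting**

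A subject can stop a given study only once, so repeats cannot enter a by-study row. In the any-study row, k repeat stoppers add k/N. Five in the 340 mg column at PD302 = 250 add 5/333 = 1.5 to 5/250 = 2.0 percentage points, which is upward.

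**The case against.** The best defence is that the by-study rows only break down the pooled total by source study. With one column N and every event counted, they add up to the any-study row. The note states the denominator, each cell prints its count, and Table 1.1.3 gives Kaplan-Meier time to discontinuation by column. This explains the layout. It does not stop the stated rule from printing unlike percentages side by side for arms randomised 1:1. Elsewhere the SAP uses a category-specific denominator when it wants one: the shells for adverse events by subgroup, such as Table 1.6.1.3, divide by the subgroup within the treatment.

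On repeats, Section 8.1 openly plans event counting with a footnote and can be read as an exception to Section 7.2. Few repeats are likely in Table 1.1.1, because Groups 1 and 2 must have completed the earlier study's visits (Protocol Sections 7.1.1 and 7.1.2), and those who stopped for events related to ADS-5102 are excluded (7.2.1 and 7.2.2). Repeats remain possible in Table 1.1.2, since subjects who stopped drug were encouraged to complete assessments. A subject who moves from placebo to 340 mg and stops both repeats only in the All column. What stands against the plan is narrower: a row labelled as subjects that counts events, and a promised footnote missing from the shells.

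A reader might infer that double counting helps to push the ADS-5102 percentages down. It does not: it is absent from the by-study rows and raises the any-study and reason rows.

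**Conclusion.** The denominator fault holds. In the PD301 row every ADS-5102 column is deflated relative to placebo, about three- to fourfold at the planned PD302 size and about two- to threefold if PD302 is near 150. The AM201 row of the 340 mg column behaves similarly.

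A reader might extend this to every by-study active percentage. The figures do not support that. In the AM201 row the pooled ADS-5102 column may be only modestly lower than placebo, or higher, depending on PD302 size and roll-over. The PD302 row offers no comparison, and the any-study row properly uses the pooled N.

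The sizes rest on all randomised subjects having been dosed, and on assumed PD302 numbers and roll-over. For the PD301 row, the direction is the same across the whole range examined. The effect is on descriptive reading only. The event count under a subjects label is a separate and smaller inconsistency with Section 7.2.

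**What to change.** - In the three by-study rows of Tables 1.1.1 and 1.1.2, print the number treated in that study and column and use it as the denominator, or print counts without percentages. State this in the note.
- Mark the PD302 placebo cell as not applicable.
- Count each subject once per column in the any-study row. Keep all events in the reason rows, so that no stop or its reason is lost, and say that those rows count events and may sum to more than the any-study row.
- Add to both shells the multiple-discontinuation footnote planned in Section 8.1.

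The cost is an edit to two shells and their notes, with matching programming. Study-level Ns are already held and no new data are needed.
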